### **Privacy Concerns**

Data downloaded from the CGM will be collected for the study as measures of diabetes self-management behaviors. Some people may be uncomfortable with the researchers' having such detailed information about their daily diabetes habits, however this too is part of routine diabetes care. The group setting of the SMA removes much of the privacy that is provided to patients and their families during a routine individual visit. Some families might feel uncomfortable talking about personal experiences or attitudes related to their own diabetes care in front of other people. Description of the SMA will be clear during the consent process so that only families who are comfortable sharing in a group setting will choose to participate in the study. Participants and their caretakers will also have the option to withdraw from the intervention at any time if they become uncomfortable with the lack of privacy in the SMA.

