### **5.7 End of Participation Criteria and Procedures**

Participants are free to withdraw from participation in the study at any time upon request. The reason for participant discontinuation or withdrawal from the study will be recorded on the Premature Termination Case Report Form (CRF). Subjects who sign the informed consent but do not receive the study intervention may be replaced. Subjects who sign the informed consent form, begin the study intervention, and subsequently withdraw, or are withdrawn or discontinued from the study, will try and be replaced.

Participants who experience significant psychological distress as a result of the intervention or whose presence at SMA visits will be terminated from study participation. Anyone experiencing psychological distress will be referred to the diabetes psychology team for support (Drs. [name] and [name], Co-I's).

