#### Follow up SMA at 3, 6, 9, and 12-months

Follow up SMA will be scheduled 3, 6, 9 and, 12 months from the initial group visit. Data will be collected from routine clinical care, including height, weight, BMI, and a point of care fingerstick A1c. Survey measures will be completed again as described previously. CGM data will be analyzed for the 14 days preceding each visit. Chart review from the time of the initial baseline visit will be conducted to assess the incidence of DKA, severe hypoglycemia, ED visits, and hospital admissions. Details obtained from the chart review will be confirmed with participants. Data from the CGM will be obtained through online software used to securely query these devices for routine clinical care (Dexcom Clarity).

Discussions and education guided by the facilitators will focus on issues that have been described in the literature as potential barriers to CGM use and adherence. Recurrent alerts and alarms can result in alarm fatigue, and falsely low glucose readings and sensor or transmitter failures have been cited as reasons for discontinuing CGM use. The continuous nature of CGM data has been shown to place significant demands on patients and their families, and to create stress related to the constant need for

diabetes-related attention. Follow up visits will focus on optimized use of CGM alarms and prevention of alarm fatigue. Psychologists and CDCES will discuss strategies to cope with the on-body presence and potential embarrassment resulting from CGM wear and to optimize parent-child communication surrounding CGM. Nutritionists will highlight the impact of different foods on glycemic trends and discuss strategies to optimize control. SMA will also allow ample opportunity to jointly review deidentified CGM reports and how to effectively interpret data and make management changes in response to CGM data, empowering patients and families to improve self-management and reduce stress related to CGM use. Active participation in discussions and group exercises will continue to strengthen the community feeling and social support network within the SMA group. Any participant that chooses to discontinue CGM during the 12 month study period will wear a blinded CGM 10 days prior to the follow up visits to allow for complete data collection.

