If a visit is missed by the participant, he/she will have the option to attend a different group's SMA that corresponds to the same timing as the SMA that was missed. In the event of withdrawal or early termination, participants will be asked to come for an end of study visit. If any participant chooses to discontinue CGM use, they will be asked to wear a blinded CGM for each of the 10 day periods ahead of their planned clinic visits.

Upon completion of the final SMA visit at month 12, dyads will be contacted to schedule a semi-structured interview and will then return to standard clinical care. A structured focus group guide consisting of broad, open-ended questions to elicit details from patients and parents will be provided to facilitators. These sessions will last 45 minutes ( $\pm$  15 minutes). The sessions will be recorded on two separate devices and subsequently transcribed to allow for data analysis.

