## **6.4 Description of Study Procedures/Evaluations**

### **Study Visits**

All SMA appointments will be scheduled at the time that consent is obtained. Biometric data (height, weight, BMI, A1c) will be obtained as part of routine care. Data from 14 days prior to the visit for the CGM will be obtained through online software used to securely query these devices for routine clinical care (Dexcom Clarity). Secure REDCap surveys will be sent to participants via email 1 week before their visit (including the T1DAL, DSMP, SEDS, PAID, CGM Benefits and Burdens, and an SMA evaluation for patients; and for parents: P-T1DAL, P-DSMP, P-SEDS, and P-PAID, CGM Benefits and Burdens, and SMA evaluation). If the surveys have not been completed at the time of the visit participants will be given the option to complete the measures using an iPad or paper surveys in clinic at the time of their visit.

Prior to the study visit, chart review will be conducted to assess the interval incidence of DKA, severe hypoglycemia, ED visits, and hospital admissions. This will be conducted in accordance with the HIPAA rules. Information obtained through chart review will be

corroborated with patients during study visits to ensure accuracy. Biometric data, CGM data obtained from Clarity, and A1c values will be provided to participants as part of routine clinical care. The results from the battery of questionnaires will not be provided to patients.

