### **8.3 Analysis Datasets**

Data analysis will be conducted according to a per-protocol analysis as we will be unable to obtain appropriate data from those who withdraw from the study. Participants with incomplete data will be included in analyses when possible.

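### Section 8.3 justifies an undefined per-protocol set by saying leavers' data cannot be had; this conflicts with Sections 6.3 and 6.4 and may flatter the secondary 12-month changes

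*Combined protocol and SAP*

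**What the plan says.** Section 8.3 chooses a per-protocol set and gives a single reason for it: "we will be unable to obtain appropriate data from those who withdraw from the study". A second sentence adds a qualifier: "Participants with incomplete data will be included in analyses when possible". The section does not say what makes a child per-protocol, and no all-starter or sensitivity analysis is planned.

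Other sections bear on whether leavers' data can be had:

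- Section 6.3 (follow-up SMA visits): "In the event of withdrawal or early termination, participants will be asked to come for an end of study visit". The measurements at that visit are not listed.
- Section 6.3, on the follow-up visits: "Data will be collected from routine clinical care, including height, weight, BMI, and a point of care fingerstick A1c". Section 6.4 repeats the point: "Biometric data (height, weight, BMI, A1c) will be obtained as part of routine care". Both sections take follow-up CGM data from the download software already used in the clinic, and take DKA, severe hypoglycemia, ED visits and admissions from chart review.
- Section 2.3 (Privacy Concerns) gives families the "option to withdraw from the intervention at any time", which is not the same as leaving the study.

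Two rules affect who ends up in the analysis. Section 8.4 handles missing data by casewise deletion. Section 5.7 says that those who "begin the study intervention, and subsequently withdraw, or are withdrawn or discontinued from the study, will try and be replaced"; Section 8.5 repeats the intention to replace.

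**The concern.** Hypotheses 2a to 2c in Section 8.2 are within-group changes from baseline to 12 months. With no control arm, any selection of who contributes a 12-month value passes straight into the estimate. If the families who leave are those doing less well, a set made up mainly of stayers shows a better change than the model of care produced in those who began it.

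The protocol itself gives reasons why leaving could be related to outcome. Section 2.3 foresees families leaving because they are uncomfortable in the group, and Section 5.7 ends participation for significant psychological distress caused by the intervention. Quality of life and diabetes distress are among the outcomes. Section 2.4 expects the results to inform later randomized studies, so a flattering estimate could be carried forward. Nothing else in the plan guards against this: Section 8.1 says there is no formal SAP, and Section 8.6 treats measures against bias as not applicable.

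**Working it through.** **Step 1. Does the stated reason hold?** Set each type of secondary outcome against the source the protocol describes.

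| Outcome | Source in the protocol | Could a leaver's value be obtained? |
|---|---|---|
| A1c | Routine care (6.3, 6.4) | Yes, if the child stays in clinic and consent allows |
| CGM metrics, child using CGM clinically | Clinic download software (6.3, 6.4) | Yes, on the same conditions |
| DKA, severe hypoglycemia, ED visits, admissions | Chart review (6.3, 6.4) | Yes, on the same conditions |
| CGM metrics, child who stopped CGM | Blinded sensor, a study procedure (6.3) | Only through the end-of-study visit, if that visit includes it |
| Surveys | REDCap, a study procedure (6.4) | Only through the end-of-study visit, if that visit includes them |

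So the reason in 8.3 is contradicted for the first three rows. For the last two it is only put in doubt.

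**Step 2. Does the rest of the plan bring leavers back in?** The sentence on incomplete data could admit a leaver's earlier visits, and a mixed model with a random subject effect can use them. But it gives no rule and does not mention leavers, and 8.4 does not say whether casewise deletion removes a visit or a whole child. The text therefore leaves open anything from stayers only to all visits of all starters.

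**Step 3. How large could the effect be?** The documents give no effect size, SD, significance level or dropout rate (Section 8.5 says only that dropout should be low), so there is no figure of the plan's own to reproduce. What follows is an illustration.

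*Number of leavers.* Retention must exceed 80% of 20. 16/20 = 80% does not; 17/20 = 85% does. At most 3 can leave with the benchmark met.

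*Formulas.*
- All-starter mean = (stayers × their mean change + leavers × their mean change) / all starters.
- Overstatement = (leavers / all starters) × (mean change in stayers − mean change in leavers).

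*Assumed:* +8 TIR points in stayers.
- Leavers change by 0: (17×8 + 3×0)/20 = 136/20 = 6.8. Overstated by 8 − 6.8 = 1.2 points; 1.2/6.8 = 18%.
- Leavers change by −5: (17×8 − 15)/20 = 121/20 = 6.05. Overstated by 1.95 points; 1.95/6.05 = 32%.

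*Range.* For a stayer-leaver gap of 5 to 20 points with 3 leavers, the overstatement is 0.15×5 = 0.75 to 0.15×20 = 3.0 points. For a gap of 0 it is 0.

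*With replacement.* If 3 leave and are replaced so that 20 complete, there are 23 starters.
- Leavers at 0: 160/23 = 6.96, overstated by 1.04 points (15%).
- Leavers at −5: 145/23 = 6.30, overstated by 1.70 points (27%).

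The bias is slightly smaller, because leavers are a smaller share of starters, but the analysed group again numbers 20 and the loss is less apparent.

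*Effect on a test.* In a simulation of 20,000 runs with no true change, 20 starters, 3 leavers and a correlation of 0.3 to 0.7 between leaving and poorer change, a two-sided t-test in stayers at an assumed 5% level rejected in 6.1% to 13.5% of runs.

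**The case against.** The strongest defence is that 8.3 goes on to include incomplete data where it can, and that 8.4 plans models able to use partial follow-up. A reader might infer that collected data are thrown away and that only stayers are analysed. The documents do not go that far: the set is undefined and the text is ambiguous. That stands, but an ambiguous rule still needs repair, and casewise deletion points towards exclusion.

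A reader might also take the end-of-study visit as scheduled and as proof that 12-month data will exist. It is only requested, its content is not stated, and it falls whenever the family leaves. Nor does the routine-care argument reach the surveys or blinded CGM. Being able to see A1c or CGM data in the clinic is not permission to use them after withdrawal; that depends on consent terms that are not in the text reviewed. Leaving the intervention (2.3) and leaving the study (8.3) are different events, and the protocol describes a return to individual care only after month 12. All of this stands and limits the point.

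It is tempting to say that the bias is certain and favourable. The documents do not show that. Barriers to attendance (5.6) may be unrelated to outcome, and then there is no bias. It is equally tempting to treat a 20% loss as the plan's own figure; the benchmark is strictly above 80%, so 4 of 20 would fail it.

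Finally, these are secondary, preliminary outcomes in a small uncontrolled pilot. Retention is itself reported, Table 2 tabulates missing A1c, CGM and survey data, and Section 8.4 lists individual data, so attrition would be visible. That limits the harm but does not correct the estimates.

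**Conclusion.** The point holds in a limited form. The sole reason given for the per-protocol set conflicts with the protocol's own request for an end-of-study visit and with its routine-care sources for A1c, clinical CGM and chart events. Because the set is undefined, the secondary 12-month changes may be estimated mainly in stayers. If leaving is related to poorer change, they will look too favourable, with TIR and quality of life too high and A1c too low.

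The size cannot be determined from the documents. The 1.2 and 1.95 points shown above rest on assumed changes and on 3 leavers of 20. The primary feasibility outcome is not affected, since retention counts leavers directly. This should be changed, but it bears on how the preliminary changes are interpreted, not on the study's main aim.

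**What to change.** For the secondary outcomes, replace Section 8.3 with the following:

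- Analyse all children who attended at least one SMA. Use every available assessment in the mixed model, including the end-of-study visit, and do not drop a whole child for a missed visit. Amend the casewise-deletion wording in 6.4 and 8.4 to match.
- Count replacements as additional starters, not as substitutes for those who left.
- Define the per-protocol set and keep it as a sensitivity analysis.

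In Section 6.3, state what the end-of-study visit collects, in particular whether surveys and CGM are included. In Section 5.7, separate stopping the SMA from withdrawing permission for data. For children who only stop the SMA, continue to extract routine-care A1c and CGM data at the planned times where consent allows.

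The cost is mainly wording in 8.3, 5.7 and 6.3, with the matching edit on casewise deletion. Continued extraction may need a consent amendment; Section 10.2 requires IRB approval for that and leaves re-consent to the IRB. The estimates may become less favourable.

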### **8.4 Description of Statistical Methods**

#### **General Approach**

Descriptive measures will be used to summarize participant demographic information. P-values and confidence intervals will be two-tailed. Covariates will be pre-specified. Tests to assess normality will be performed and data transformation or non-parametric analyses will be used when necessary.

#### **Analysis of the Primary Efficacy Endpoint(s)**

We will track recruitment, enrollment, participation, and retention through a CONSORT table (Table 2) for the intervention group. Feasibility benchmarks include: recruitment (>60% of reached/eligible participants), CGM initiation, (>80%), SMA sessions attended (>80%), and retention (>80%). In addition, feasibility encompasses demographic characteristics of the enrolled sample, with enrollment and overall increased uptake of CGM among youth from historically underrepresented racial and ethnic backgrounds

(Black race and/or Latinx ethnicity) and income levels. Attrition data and team feedback will help determine how recruitment rates may be improved. Acceptability will be assessed using satisfaction surveys and determined by a high level of satisfaction with participation, perceived utility of the intervention content, and perceived benefit from participation (>80% reporting that they were satisfied and perceived utility and benefit). We will report summary statistics on each feasibility and acceptability item in the questionnaires (mean and standard deviation well as percent answering a specific Likert level). Acceptability also will be examined by key demographic characteristics, including participant age and race/ethnicity.

Parent-child dyads will participate in semi-structured interviews to assess satisfaction with the SMA. Thematic analysis of qualitative data will be conducted by two team members who will independently review interview transcripts to generate initial codes. Initial codes will be discussed by the group to generate a list of second-cycle codes and each team member will then apply the coding framework to all transcripts before identifying dominant themes. ATLAS.ti software will be used to organize and analyze the qualitative data.

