### 3.3 Primary Outcome Measure(s)

Given the novelty of the SMA approach for underserved youth and promotion of CGM technology uptake and sustained use, feasibility and acceptability of the intervention will serve as the primary outcome measure. We will track recruitment, enrollment, participation, and retention through a CONSORT table (Table 2) for the intervention group. Feasibility benchmarks include: recruitment (>60% of reached/eligible

participants), CGM initiation, (>80%), SMA sessions attended (>80%), and retention (>80%). In addition, feasibility encompasses demographic characteristics of the enrolled sample, with enrollment and overall increased uptake of CGM among youth from historically underrepresented racial and ethnic backgrounds (Black race and/or Latinx ethnicity) and income levels. Attrition data and team feedback will help determine how recruitment rates may be improved. Acceptability will be assessed using satisfaction surveys and determined by a high level of satisfaction with participation, perceived utility of the intervention content, and perceived benefit from participation (>80% reporting that they were satisfied and perceived utility and benefit). We will report summary statistics on each feasibility and

acceptability item in the questionnaires (mean and standard deviation as well as percent answering a specific Likert level). Acceptability also will be examined by key demographic characteristics, including participant age and race/ethnicity.

Parent-child dyads will participate in semi-structured interviews to assess satisfaction with the SMA. Thematic analysis of qualitative data will be conducted by two team members who will independently review interview transcripts to generate initial codes. Initial codes will be discussed by the group to generate a list of second-cycle codes and each team member will then apply the coding framework to all transcripts before

**Table 2.** Analytical plan for Aim 1, feasibility and acceptability.

Construct	Measure	Interval
Recruitment	# referred	Study initiation through completion of recruitment
Feasibility/	# screened	
Acceptability	# enrolled % eligible who enroll	
Intervention	#/% sessions attended	SMA visits every 3mo
Feasibility		
Intervention	Child/parent satisfaction ratings	After completion of intervention
Acceptability	Child/parent qualitative interview	
Retention	% who initiate CGM	All assessment time points

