**Follow Up SMA:** Follow up SMA will be scheduled 3, 6, 9, and 12 months from the initial group visit. CGM data from 14 days prior to each SMA will be reviewed by the endocrinologist ahead of the group visit. Discussions and education guided by the facilitators will focus on issues that have been described in the literature as potential barriers to CGM use and adherence. Recurrent alerts and alarms can result in alarm fatigue, and falsely low glucose readings and sensor or transmitter failures have been cited as reasons for discontinuing CGM use. The continuous nature of CGM data has been shown to place significant demands on patients and their families, and to create stress related to the constant need for diabetes-related attention. Follow up visits will focus on optimized use of CGM alarms and prevention of alarm fatigue. Psychologists and CDCES will discuss strategies to cope with the on-body presence and potential embarrassment resulting from CGM wear and to optimize parent-child communication surrounding CGM. Nutritionists will highlight the impact of different foods on glycemic trends and discuss strategies to optimize control. SMA will also allow ample opportunity to jointly review de-identified CGM reports and how to effectively interpret data and make management changes in response to CGM data, empowering patients and families to improve self-management and reduce stress related to CGM use. Active participation in discussions and group exercises will continue to strengthen the community feeling and social support network within the SMA group. Any participant that chooses to discontinue CGM during the 12 month study period will wear a blinded CGM 10 days prior to the follow up visits to allow for complete data collection. Upon completion of the final SMA visit at month 12, dyads will be contacted to schedule a semi-structured interview and will then return to standard clinical care.

**3-Month and 6-Month Post-Intervention Follow-Ups:** Survey measures and assessments of glycemic control will be repeated after 3 months and 6 months of routine clinical care to assess for long-lasting effects of the intervention.

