### **8.2 Statistical Hypotheses**

Primary Outcome: feasibility and acceptability of SMA among underserved youth with T1D.

Hypothesis 1a. Rates of SMA retention (>80%) at 12-months and satisfaction with visits (>80%) will be high.

Null Hypothesis 1a: n/a

Hypothesis 1b: Thematic analysis of semi-structured interviews will identify high satisfaction with SMA.

Null Hypothesis 1b: n/a

Secondary Outcome: preliminary impact of SMA on glycemic control, self-management skills, self-efficacy, diabetes related quality of life, and treatment satisfaction among underserved children with T1D and their caregivers

Hypothesis 2a: CGM percentage wear time and sustained use, as defined by use within the 2 weeks prior to the visit, will be greater upon completion of the SMA intervention at 12 months compared to baseline

Null Hypothesis 2a: CGM percentage wear time and sustained use, as defined by use within the 2 weeks prior to the visit, will not be significantly different upon completion of the SMA intervention at 12 months

Hypothesis 2b: CGM time in range (70-180 mg/dL) will be greater and the glucose management indicator (GMI) lower for youth upon completion of the SMA intervention group at 12 months compared to baseline.

Null Hypothesis 2b: CGM time in range (70-180 mg/dL) will not be significantly different upon completion of the SMA intervention at 12 months

Hypothesis 2c: Diabetes-specific quality of life, self-management behaviors, and self-efficacy scores will be greater upon completion of the SMA intervention at 12 months compared to baseline.

Null Hypothesis 2c: Diabetes-specific quality of life, self-management behaviors, and self-efficacy scores will not be significantly different upon completion of the SMA intervention at 12 month

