## **8.5 Sample Size**

As this is a pilot study, we plan to enroll up to 20 parent-child dyads. We anticipate low dropout rates, but do plan to enroll new subjects to keep the total number of subjects at up to 20 in case of attrition. If there is a sufficient number of new subjects enrolled to replace those that drop out, a new SMA group will be created so that newly enrolled subjects will be able to start the intervention from the baseline visit.

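### The >80% primary benchmarks are judged on observed percentages from up to 20 dyads, with no interval and with a denominator that can leave out replaced dropouts

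*Combined protocol and SAP*

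**What the plan says.** Feasibility and acceptability are the primary outcome (Sections 3.3, 6.4 and 8.4). The feasibility benchmarks are recruitment above 60%, CGM initiation above 80%, and "SMA sessions attended (>80%), and retention (>80" per cent). Acceptability requires more than 80% to report satisfaction, utility and benefit. Hypothesis 1a in Section 8.2 reads "Rates of SMA retention (>80%) at 12-months and satisfaction with visits (>80%) will be high", followed by "Null Hypothesis 1a: n/a".

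On reporting, Section 3.3 says "We will report summary statistics on each feasibility and" acceptability item, meaning mean, standard deviation and percentage, alongside a CONSORT table. The General Approach in Section 8.4 says that intervals will be two-tailed. It gives no confidence level and does not link intervals to the benchmarks. Section 8.1 states that there is no separate SAP.

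On size, Section 8.5 says "As this is a pilot study, we plan to enroll up to 20 parent-child dyads" and that the investigators "do plan to enroll new subjects to keep the total number of subjects at up to 20 in case of attrition". Section 5.7 also provides for replacing participants who withdraw after starting the intervention. Section 8.3 specifies a per-protocol analysis, because suitable data are not expected from those who withdraw, and includes participants with incomplete data where possible.

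On sessions, there is an initial SMA, and "Follow up SMA will be scheduled 3, 6, 9, and 12 months from the initial group visit", so each dyad has five. Table 2 lists the number and percentage of sessions attended without defining the unit or the denominator.

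**The concern.** The only stated basis for the primary conclusion is whether an observed percentage lies above a line. With about 20 dyads that percentage is imprecise, and nothing in the planned output tells the reader how imprecise. A report that retention exceeded 80% could be taken as evidence about the true rate when the data are also compatible with a much lower one.

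The denominator is a second problem, and it acts in one direction. If dyads who withdraw leave the analysis set and new ones take their place, the remaining group is selected for having stayed. Retention and attendance are the quantities most affected by that selection.

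Section 2.4 expects the results to inform the design of later randomised trials. Overstated attendance or retention would feed into their sample size and dropout assumptions.

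**Working it through.** The plan gives no precision or power figure, so there is none to reproduce.

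**Inputs.** n = 20 dyads, the maximum in Section 8.5. Threshold strictly above 80%, from Sections 3.3 and 8.4. Five sessions per dyad, from Section 4. The 95% confidence level is an assumption, since the documents give none.

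**Step 1: smallest pass.** 16/20 = 80.0%, which is not above 80%. 17/20 = 85.0% is the first count that passes.

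**Step 2: interval at the smallest pass.** The exact (Clopper-Pearson) lower limit L solves P(X ≥ 17 | 20, L) = 0.025, and the upper limit U solves P(X ≤ 17 | 20, U) = 0.025.

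| Observed | Rate | Exact 95% interval |
|---|---|---|
| 17/20 | 85% | 62.1% to 96.8% |
| 18/20 | 90% | 68.3% to 98.8% |
| 19/20 | 95% | 75.1% to 99.9% |
| 20/20 | 100% | 83.2% to 100% |

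Only 20/20 has a lower limit above 80%. For 17/20, a Wilson 95% interval has a lower limit of 64.0%, and an exact 90% interval 65.6%. The choice of method or level does not change the conclusion.

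**Step 3: chance of passing.** P(X ≥ 17) = Σ C(20,k) p^k (1−p)^(20−k), for k = 17 to 20. At p = 0.80 the terms are 0.205 + 0.137 + 0.058 + 0.012 = 0.41 after rounding.

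| True rate | P(at least 17/20) |
|---|---|
| 70% | 0.11 |
| 75% | 0.23 |
| 80% | 0.41 |
| 85% | 0.65 |
| 90% | 0.87 |

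**Step 4: other denominators.** If satisfaction is pooled over 40 children and parents, the smallest pass is 33/40 = 82.5%, with an exact interval of 67.2% to 92.7%, ignoring pairing. If attendance is pooled over 20 × 5 = 100 sessions, the smallest pass is 81/100, with a naive interval of 71.9% to 88.2%. The naive interval is too narrow if attendance is correlated within a dyad. All these intervals extend well below 80%.

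**Step 5: effect of the denominator (assumed figures).** Suppose 20 dyads complete and attend 90% of sessions, and 5 others withdraw after 1 of 5 sessions and are replaced. The 20 completers include the replacements.

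- Attendance per protocol: 90/100 = 90%.
- Attendance over all enrolled: (90 + 5)/(100 + 25) = 95/125 = 76%.
- Retention per protocol: 20/20 = 100%, by construction.
- Retention over all enrolled: 20/25 = 80%, which is not above 80%.

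In this example both benchmarks are met on one denominator and missed on the other.

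**The case against.** The strongest reply is that this is a pilot. Wide intervals are unavoidable at n = 20, no null hypothesis is stated for the primary outcome, and the plan nowhere claims that a pass proves a true rate above 80%. The benchmarks stand beside demographic reach, attrition data, team feedback and interviews. The General Approach already foresees two-tailed intervals, and anyone could compute one later from the counts. The CONSORT table would also show withdrawals, and Section 8.3 keeps incomplete participants where possible. All of this stands, and it makes the matter one of reporting and definition, not an invalid design. It does not answer the point that the primary result is planned without an interval, or that the denominator is left open.

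A reader might infer three stronger things that the documents do not support:

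- **That a go decision for a larger trial rests on the benchmarks.** No such rule is written. Section 2.4 says only that results should inform future designs. Section 7.2 lists meeting the primary endpoint and futility among possible grounds for halting, but ties neither to these percentages.
- **That the threshold should read at least 80%.** Strictly above 80% is a legitimate choice. Accepting 16/20 would raise the chance of passing from 0.41 to 0.63 at a true 80%, but also from 0.11 to 0.24 at a true 70%.
- **That a child who attends 4 of 5 sessions fails.** This holds only if attendance is scored per child, which the plan does not say. Pooled over sessions, the steps are much finer and no single missed visit decides the result.

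**Conclusion.** The concern holds as a matter of precision and denominator. At 20 dyads, the smallest passing result for a per-dyad benchmark is compatible with a true rate as low as 62%, and a programme with a true rate of 70% would pass about one time in nine. Only a perfect 20/20 would place the lower limit above 80%.

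The per-protocol set combined with replacement can raise observed attendance and retention. The 14-point gap in attendance (90% against 76%) illustrates the mechanism and does not predict what will happen.

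These figures rest on n = 20, independent dyads, an assumed 95% level, and a reading of per protocol as excluding those who withdraw. Fewer dyads would move the smallest pass slightly (15/18 or 16/19) without removing the problem. The illustration also assumes that more than 20 dyads can be consented. Sections 5.7 and 8.5 imply this through replacement, although the Protocol Summary gives an accrual ceiling of 20.

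**What to change.** In Sections 3.3 and 8.4, with a matching exception in 8.3:

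1. Keep the threshold strictly above 80% unless the sponsor deliberately chooses otherwise.
2. Define attendance as sessions attended divided by sessions due, with five sessions due for every enrolled dyad, including those who withdrew and were replaced. Define retention over the same dyads. Exempt both from the per-protocol rule in Section 8.3. Attendance and withdrawal are known for dropouts without further data from them.
3. Report a 95% interval beside each benchmark: exact for proportions of dyads, clustered by dyad for sessions, and allowing for child-parent pairing if satisfaction is pooled.
4. Word the conclusion as benchmark met or not met, with the true rate compatible with X% to Y%.

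The cost is a few sentences and one column in the feasibility table. No extra participants, visits or data are needed. The drawback is that attendance and retention may come out lower, and the result will read as less definitive.
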